6.2. Preparation/Handling/Storage/Accountability

Combination Products

For this protocol, the term combination product refers to the single integral drug-device combination.

The Sponsor-manufactured combination product for use in this study is the pre-filled syringe (PFS) assembled in ar Additional details on the guselkumab Investigator Brochure.

All combination product deficiencies (including failure, malfunction, improper or inadequate design, manufacturer error, use error, and inadequate labeling) shall be documented and reported by the investigator throughout the study as product quality complaints (PQC, see Section 10.4.6).

Preparation/Handling/Storage

For controlled temperatures ranging from 36°F to 46°F (2°C to 8°C). sterile liquid in a single-dose sterile liquid in a single-dose sterile liquid in a single-dose administration, placebo will be supplied as a 1 mL sterile liquid in a single-dose All study intervention must be stored at controlled temperatures ranging from 36°F to 46°F (2°C to 8°C).

Guselkumab and placebo for guselkumab should be a clear and colorless to light yellow solution that may contain translucent particles. Do not use guselkumab or placebo for guselkumab if the liquid is cloudy or discolored or has large particles. Protection from light is not required during the preparation and administration of the study intervention material but avoid direct exposure to sunlight. Aseptic procedure must be used during the preparation and administration of the study intervention material.

Study drug may be administered at the study site or at home by the trained participant or their caregiver (without a study visit) and will be routinely done beginning at Week 56. Study personnel will instruct participants on how to transport, store, and administer study intervention for at-home use as indicated for this protocol.

The study intervention may be delivered directly to the participants from the site by a courier, if needed. Each courier will adhere to privacy requirements approved by the Independent Ethics Committee (IEC)/Institutional Review Board (IRB). The capability to utilize these direct-to-patient shipments will be assessed by the sponsor to ensure that it is allowable per local regulations.

Refer to the study Site Investigational Product and Procedures Manual for additional guidance on study intervention preparation, handling, and storage

Accountability

The investigator is responsible for ensuring that all study intervention received at the site is inventoried and accounted for throughout the study. All study intervention will be stored and disposed of according to the Sponsor's instructions. Study site personnel must not combine contents of the study intervention containers.

Study intervention must be handled in strict accordance with the protocol and the container label, and must be stored at the study site in a limited-access area or in a locked cabinet under appropriate environmental conditions. Unused study intervention must be available for verification by the Sponsor's study site monitor during on-site monitoring visits. The return to the Sponsor of unused study intervention will be documented on the intervention return form. When the study site is an authorized destruction unit and study intervention supplies are destroyed on-site, this must also be documented on the intervention return form.

Potentially hazardous materials such as used ampules, needles, syringes and vials should be disposed of immediately in a safe manner and therefore will not be retained for intervention accountability purposes.

The dispensing of study drug to the participant, and the return of study drug from the participant, must be documented on the drug accountability form. Participants must be instructed to return all original containers, whether empty or containing study drug.

Study intervention should be dispensed under the supervision of the investigator or a qualified member of the study site personnel, or by a hospital/clinic pharmacist. Study intervention will be supplied only to individuals participating in the study. Returned study intervention must not be dispensed again, even to the same participant. Study intervention may not be relabeled or reassigned for use by other participants. The investigator agrees neither to dispense the study intervention from, nor store it at, any site other than the study sites agreed upon with the Sponsor. Further guidance and information for the final disposition of unused study interventions are provided in the Site Investigational Product and Procedures Manual.

Since, once they are trained, participants may potentially be self-administering study drug at home, they will receive detailed instructions for study drug storage and disposal of used syringes and handling of unused study material. Participants will receive a sharps container to dispose of used syringes. Participants will be instructed to return the sharps container and/or unused cartons with syringes. Participants will record study drug administrations with time and date information in their participant diary.

6.3. Measures to Minimize Bias: Randomization and Blinding

Intervention Allocation

Procedures for Randomization and Stratification

Central randomization will be implemented in this study. At Week 0, participants will be randomly assigned to 1 of 2 intervention groups in a 1:1 ratio (see Section 4.1) based on a

computer-generated randomization schedule prepared before the study by or under the supervision of the sponsor. The randomization will be balanced by using randomly permuted blocks and will be stratified by clinical remission status at baseline (CDAI < 150, CDAI \geq 150), region (North America, Western Europe, rest of world) and number of prior surgeries (1 surgery versus > 1 surgery, with the qualifying surgery counting as 1 surgery). The IWRS will assign a unique intervention code, which will dictate the intervention assignment and matching study intervention kit for the participant.

Blinding

To maintain the study blind, the study intervention container will have a label containing the study name, study intervention number, and reference number. The study intervention number will be entered in the eCRF when the study intervention is dispensed. Each active study intervention and its matching placebo will be identical in appearance and will be packaged in identical containers. All participants will receive the same device(s), which could be either active or matching placebo at 8-week intervals to maintain treatment blinding.

The investigator will not be provided with randomization codes. The codes will be maintained within the IWRS, which has the functionality to allow the investigator to break the blind for an individual participant.

Data that may potentially unblind the intervention assignment (ie, study intervention serum concentrations, anti-guselkumab antibodies) will be handled with special care to ensure that the integrity of the blind is maintained and the potential for bias is minimized. This can include making special provisions, such as segregating the data in question from view by the investigators, clinical team, or others as appropriate until the time of unblinding.

At the Week 48 DBL (main study DBL), data will be unblinded for analysis to the sponsor only. Treatment assignment will remain blinded to the study sites and participants until the last participant completes the Week 156 evaluations.

Under normal circumstances, the investigator blind should not be broken until the Week 156 DBL is completed, unless specific emergency treatment/course of action would be dictated by knowing the treatment status of the participant. In such case, the investigator may in an emergency determine the identity of the intervention by contacting the IWRS. It is recommended that the investigator contacts the sponsor or its designee, if possible, to discuss the particular situation before breaking the blind. Telephone contact with the sponsor or its designee will be available 24 hours per day, 7 days per week. In the event the blind is broken, the sponsor must be informed as soon as possible. The date and reason for the unblinding must be documented in the appropriate section of the eCRF and/or in the source document. The documentation received from the IWRS indicating the code break must be retained with the participant's source documents in a secure manner.

Participants who have had their intervention assignment unblinded by the investigator will not be eligible to receive further study intervention, but should complete evaluations specified in the SoA (Section 1.3) for participants who discontinue study intervention.

6.4. Study Intervention Compliance

When participants have self- (or caregiver-) administration of study intervention at home, compliance with study intervention will be assessed at each visit. Compliance will be assessed via the return of boxes that contained study drug and will then be documented in the source documents and eCRF. Deviation(s) from the prescribed dosage regimen should be recorded in the eCRF.

Participants will receive instructions on compliance with study treatment when they begin self-administration of study intervention at home. When participants begin self-administration at home, the investigator or designated study personnel will maintain a log of all study intervention dispensed and returned.

When study intervention is self-administered by participants (or caregivers) at home, participants will record all study intervention administrations on a diary card.

During the study, the investigator or designated study research personnel will be responsible for providing additional instruction to reeducate any participant who is not compliant with taking the study intervention.

Compliance with the treatment schedule is strongly encouraged. It is understood that treatment may be interrupted for health-related or safety reasons. Therefore, if for any reason a participant cannot receive a dose of study intervention at the scheduled visit, the participant must make every effort to still come in for the scheduled assessments for that visit. In general, the dose should be administered within approximately 2 weeks of that scheduled visit. The participant should then resume the normal study schedule relative to the baseline visit (Week 0). In the case when a participant does not come into the investigational site for a scheduled visit, the site will follow-up with that participant. Due diligence could include telephone calls, certified letters, and email requests. Measures taken to obtain follow-up information must be documented.

Study-site personnel will keep a log of all study intervention dispensed and will compare the amount of study intervention dispensed with the amount returned.

All post-baseline visits up to and including Week 56 will have a visit window of \pm 10 days counting from Week 0 as Day 1. If a study visit occurs outside this window, the Sponsor should be consulted about how the participant should resume his or her normal dose schedule.

Information regarding study intervention administrations that are administered outside of the scheduled windows or missed will be recorded. Participant charts and worksheets may be reviewed and compared with the data entries on the eCRFs to ensure accuracy.

6.5. Dose Modification

The dose level of study treatments will not be adjusted.

CONFIDENTIAL – FOIA Exemptions Apply in U.S.

6.5.1. Open Label / Cross over Treatment

Starting after the Week 8 visit, if disease recurrence is confirmed and the definition as described in Section 9.4.3 is satisfied, participants will cross over to open-label treatment with guselkumab. Similarly, participants who are determined to have endoscopic recurrence by central read on the Week 48 or flare visit ileocolonoscopy will also cross over to open-label treatment; for the optional Week 24 ileocolonoscopy, if the central reader confirms endoscopic recurrence (modified Rutgeerts score of i2a or greater), cross over may be done at the discretion of the principal investigator with the participant's agreement. If a participant does not cross over at Week 24 for endoscopic recurrence but, within the following 16 weeks, develops an increase in CDAI \geq 70 or meets the corticosteroid-related disease recurrence criteria (see Section 9.4.3), then the participant may cross over without the need for a repeat ileocolonoscopy.

As discussed in Section 8, at the cross over visit, participants, regardless of the treatment arm to which they were randomized, will receive guselkumab for 3 doses, followed by maintenance guselkumab This regimen matches the regimen under study in the ongoing Phase 3 study, CRD3004. The induction will be open-label and the participant and investigator will remain blinded to original randomized treatment assignment. Participants will not be allowed to cross over after the Week 128 visit and, while awaiting their confirmatory ileocolonoscopy, regularly scheduled study intervention may be held.

In the event a participant meets CDAI criteria for recurrence, but endoscopic recurrence is not confirmed on ileocolonoscopy, participants will continue on assigned study intervention, and will not cross over to open-label treatment with guselkumab. At investigator discretion, a repeat evaluation, to include an ileocolonoscopy, could be performed as early as the next scheduled visit. It is recommended that such repeat assessment be undertaken only if/when there are clinical reasons to warrant such re-assessment, eg, there is worsening of symptoms and/or an increase in objective measures of inflammation such as C-reactive protein (CRP) or fecal calprotectin (and clinical criteria for recurrence must still be satisfied). In addition, if a confirmatory ileocolonoscopy was of poor quality or otherwise unreadable such that confirmatory endoscopic recurrence could not be determined, an ileocolonoscopy is recommended to be repeated as soon as feasible.

As it takes time for endoscopic disease to resolve, participants who cross over to open-label guselkumab should then be re-assessed with an ileocolonoscopy approximately 16 to 24 weeks later. At that time, it will be determined, based on investigator judgement, whether treatment with open-label SC guselkumab should be continued or not. It is recommended to include an ileocolonoscopy in this assessment.

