2.3.1. Risks for Study Participation

Potential Risks of Clinical Significance	Summary of Data/ Rationale for Risk	Mitigation Strategy	
	Risks Due to Study Intervention(s)		
Clinical Worsening of CD	The benefit-risk of guselkumab for the treatment of CD patients who have had recent ileal or ileocolonic resection has not been established.	 During the study, participants will be permitted to continue treatment of CD with certain concomitant medications (Section 6.8.1), including corticosteroids (Section 6.8.1.1). Participants will discontinue study intervention if it is not in their best interest or if they need to initiate protocol prohibited medications including certain biologics (Sections 6.8.2 and 7.1). Participants with confirmed disease recurrence, endoscopic recurrence prior to or at Week 48, or, at the investigator's discretion, with endoscopic recurrence at Week 24, will receive open-label induction treatment with guselkumab and continue maintenance treatment (Section 6.5.1). 	
Serious infections and reactivation of latent infections	Available animal and human data suggest that blockade of IL-23 may be associated with an increased infection risk. Infections that have been identified as adverse reactions to guselkumab are listed in the informed consent form.	 Discontinuation of a participant's study intervention must be considered if the participant develops a serious infection. In addition, any serious infection should be discussed with the Medical Monitor or designee, and study intervention should be withheld until the clinical assessment is complete (Section 8.4.8). Potential overlap period between prior advanced therapies and study therapy is brief (Section 5.1). Participants with a history of, or ongoing chronic or recurrent infectious disease, including human immunodeficiency virus (HIV), hepatitis B (HBV), and hepatitis C virus (HCV) will be excluded. Similarly, participants with evidence of active or untreated latent TB will be excluded from the study (Section 5.2). 	

CONFIDENTIAL – FOIA Exemptions Apply in U.S.

		 Participants who have received a live viral or bacterial vaccine within 12 weeks of baseline will be excluded from the study (Section 5.2). In addition, participants must agree not to receive a live viral or live bacterial vaccine during the study and for 12 weeks after receiving the last dose of study intervention (Section 5.3).

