proposed maintenance dose of this study, CCI , is the same as the currently approved regimen for guselkumab for the treatment of moderate-to-severe plaque psoriasis. Since psoriasis is a chronic immune mediated disease requiring long-term therapy to maintain disease control, the 2 pivotal Phase 3 studies (CNTO1959PSO3001 and CNTO1959PSO3002) included long-term extensions through a total of up to 5 years. The analyses of pooled data support the conclusion that guselkumab is well tolerated through 5 years of treatment, and the safety profile remains consistent when compared to Week 48 data, at the approved dose regimen of CCI administered CCI at Weeks 0, 4, and then CCI in adult participants with moderate to severe plaque psoriasis.

When infliximab was previously studied in this patient population in the PREVENT trial, the standard induction dosing of 5 mg/kg at Weeks 0, 2, and 6 was also not utilized. Instead, participants were immediately started on the 5 mg/kg IV q8w established maintenance regimen. While this study did not show significance for clinical recurrence at the Week 76 primary endpoint, it showed clear separation in rates of endoscopic recurrence versus placebo and in the time-to-event analysis for clinical recurrence, with the greatest separation seen in the first 6 months, supporting that it is appropriate to forgo a full induction regimen in this patient population.

In the event a participant experiences confirmed disease recurrence, endoscopic recurrence at Week 48, or, at the investigator's discretion for endoscopic recurrence at the optional Week 24 ileocolonoscopy, they will cross over to receive open-label treatment with guselkumab using the regimen under study for moderately-severely active CD in the ongoing Phase 3 study CNTO1959CRD3004. As these patients will, per protocol, have a CDAI that is ≥220 (or at a minimum is very close, at 201-219) and/or confirmed endoscopic activity, giving induction dosing of CCI for 3 doses is appropriate to treat this level of ongoing inflammatory and disease activity from CD that has recurred such that it is now in the moderately-to-severely active category.

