Study agent administration should not occur when a participant is experiencing a clinically important, active infection, an example of an appropriate reason to deviate from protocol-specified windows (which should then be documented appropriately).

The participant will be instructed to complete the CDAI daily diary through Week 152. For all visits where a score needs to be calculated in real-time, the most recent hematocrit value available will be used when calculating the CDAI score.

Flare Visit

During the study, participants who are suspected to be having a flare of disease activity (eg, example, an increase in the PRO-2 [as described in Section 8.1.2] score of at least 50 points over a 7-day period compared to baseline, or suspicion of a new fistula or abscess) can present for further evaluation at the flare visit (see SoA). This visit may include an endoscopy if it is determined that participant has a both a CDAI score of over 200 and an increase of at least 70 points over baseline.

Participants in clinical flare should undergo endoscopy, unless it can be determined without endoscopy that they have met criteria for disease recurrence (see Section 9.4.3).

Cross Over Visit

After Week 8, if a determination has been made that the participant has had a disease recurrence (by meeting the criteria outlined in Section 9.4.3 and confirmed by the central reader of i2a or greater disease when applicable) a cross over visit should be scheduled. Participants who have endoscopic recurrence confirmed by the central reader at the scheduled Week 48 ileocolonoscopy or on a flare visit ileocolonoscopy will be scheduled for a cross over visit. In addition, participants who are determined by the central reader to have endoscopic recurrence at the Week 24 (but do not have disease recurrence) can also schedule a cross over visit at the discretion of the principal investigator.

Procedures to be performed at the cross over visits are outlined in the Cross Over SoA (Section 1.3). Participants will receive their first dose of open-label guselkumab 400 mg SC at the cross over visit. Participants will then get a second dose4 weeks after the cross over visit which will be self-administered at home. The third dose will be given 8 weeks after the

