Endoscopic recurrence defined as a Rutgeerts score ≥ i2 (modified Rutgeerts ≥ i2a) has been adopted as the standard endoscopic outcome in most trials of POCD therapy (D'Haens 2008, Hanauer 2004, Hellers 1999, Reguiero 2016). The International Organization for the Study of Inflammatory Bowel Disease performed a technical review and then a 2-round vote among 14 IBD specialists using the Delphi method, and all agreed on a Rutgeerts' score of i0-i1 as the definition of postoperative endoscopic remission (Vuitton 2016). Additionally, in their recommendations for clinical trial design in POCD, an international panel of IBD experts recommended the modified Rutgeerts score as an appropriate measure of postoperative endoscopic CD activity in regulatory clinical trials (Hanzel 2021). Endoscopic recurrence has also been shown to be a strong predictor of subsequent clinical recurrence. In a meta-analysis of randomized controlled trials, the relative risk for clinical recurrence among patients who experienced endoscopic recurrence was 10.77 (95% CI 4.08-28.40). An accompanying meta-analysis of 11 cohort studies showed an even higher relative risk of 21.33 (95% CI 9.55-47.66). In addition, a single cohort study in the analysis showed a linear relationship between Rutgeerts score and clinical recurrence risk (Ble 2021).

While the study is ongoing, the modified Rutgeerts score as interpreted by the central reader will be used to determine whether endoscopic recurrence has occurred. As discussed in Section 6.5.1, cross over to open-label induction with guselkumab is permissible, at the discretion of the principal investigator, if endoscopic recurrence is confirmed on optional Week 24 ileocolonoscopy, and is mandatory after confirmed endoscopic recurrence on Week 48 ileocolonoscopy or after confirmed disease recurrence. If a participant does not cross over at Week 24 for endoscopic recurrence but within the following 16 weeks develops a CDAI in \geq 70 or meets the corticosteroid-related disease recurrence criteria (see Section 9.4.3), then the participant may cross over without the need for a repeat ileocolonoscopy. Results of the video ileocolonoscopies read by the central reader will also be the basis for the primary and secondary analyses of disease and endoscopic recurrence.

Table 3: Modified Rutgeerts Score

Score	Endoscopic Findings
i0	No lesions
i1	< 5 aphthous lesions

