9.4.3. Secondary Endpoints

The first secondary endpoint is clinical remission without disease recurrence at Week 48. The analyses of this endpoint will be performed after the test of the primary endpoint.

- Clinical remission without disease recurrence is a composite endpoint defined by the following:
 - \circ CDAI < 150 at Week 48 and
 - o No endoscopic recurrence as defined by Rutgeerts score < i2 by Week 48 and
 - o Have not experienced a disease recurrence as defined below

The second secondary endpoint is time to disease recurrence. The analyses of this endpoint will be performed after the test of the primary endpoint and the first secondary endpoint.

- Disease Recurrence is a composite endpoint defined by the following:
 - A ≥ 70-point increase from baseline in CDAI score at beyond 8 weeks after randomization; and a CDAI score of ≥ 200 and evidence of endoscopic recurrence. Endoscopic recurrence is defined as a modified Rutgeerts score of ≥ i2a at the anastomotic site or its equivalent elsewhere in the GI tract, unless a stool test for C. difficile toxin or other enteric pathogen is positive;
 - In event of a positive test for enteric pathogen including C. difficile toxin, the underlying infection should be treated and if ileocolonoscopy has not yet been performed, it should only be done when the infection has resolved, and if disease recurrence threshold is still met
 - OR initiation of a physician-prescribed corticosteroids, or an increase in the dose of steroids already being taken (by greater than 5 mg/day), for over one week for the treatment of CD and evidence of endoscopic recurrence as described above, unless a stool test for C. difficile toxin or other enteric pathogen is positive
 - OR a new draining external fistula
 - OR the reopening and draining of a previously existing external fistula
 - OR developing a new internal fistula
 - OR developing a new perianal abscess

• OR developing a new intra-abdominal abscess more than three months after the date of the index surgery

Participants who have confirmed endoscopic recurrence without disease recurrence at Week 24 or Week 48 and cross over to open-label guselkumab treatment will be censored at cross over for the time to disease recurrence endpoint.

Estimands and Estimators

Estimand of Clinical Remission without Disease Recurrence at Week 48

Treatment:

Experimental: Guselkumab at Week 0 and then thereafter through the end of the total study period.

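### Flare-visit endoscopic recurrence alone triggers crossover in Protocol 6.5.1 and Section 8 but is missing from five other route lists, and the censoring rule for time to disease recurrence does not cover it

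*Protocol*

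**What the plan says.** **Flare visit.** Protocol 6.5.1 states that participants "determined to have endoscopic recurrence by central read on the Week 48 or flare visit ileocolonoscopy will also cross over". The cross over visit text in Section 8 likewise says that those with centrally confirmed endoscopic recurrence "on a flare visit ileocolonoscopy will be scheduled for a cross over visit". Neither attaches a CDAI condition.

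Section 8.1.3 says crossover "is mandatory after confirmed endoscopic recurrence on Week 48 ileocolonoscopy or after confirmed disease recurrence". Section 4.3 opens its list "In the event a participant experiences confirmed disease recurrence, endoscopic recurrence at Week 48, or" and then adds discretionary Week 24 crossover. The synopsis (1.1), Section 4.1 and SAP 1.2.1 give the same three routes. None of these five places names the flare visit.

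**After a Week 24 recurrence without crossover.** Section 6.5.1 allows crossover without repeat ileocolonoscopy if the participant "within the following 16 weeks, develops an increase in CDAI" of at least 70 points. Section 8.1.3 repeats the sentence as "within the following 16 weeks develops a CDAI in", followed by the threshold of 70. Neither says what the rise is measured from.

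**Disease recurrence.** The CDAI arm in 9.4.3 requires a rise of at least 70 points from baseline "and a CDAI score of ≥ 200 and evidence of endoscopic recurrence". It does not apply if a stool test for an enteric pathogen is positive. The corticosteroid arm carries the same exception.

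**The concern.** Crossover moves a participant from blinded randomised drug to open-label guselkumab induction. If the sections disagree on who qualifies, two sites can handle identical participants differently and each can point to the protocol.

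The analysis uses crossover in several ways. It is a composite failure for some endpoints and a censoring event for others, and SAP Appendix 4 makes both a missed crossover and an unjustified one a major deviation. Those uses need a single definition of who should cross over.

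**Working it through.** The plan states no figure on this point, so the check sets the passages side by side and follows cases through them.

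**Step 1: flare-visit cases.** Section 8 has two sentences on flare endoscopy. One says it may be done when CDAI is over 200 and has risen at least 70 from baseline. The next says participants in clinical flare should have it unless disease recurrence can be established without it, with no CDAI gate.

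| Flare visit, central read i2a, no fistula, abscess or steroid event | Disease recurrence (9.4.3)? | 6.5.1 and Section 8 | 1.1, 4.1, 4.3, 8.1.3, SAP 1.2.1 |
|---|---|---|---|
| CDAI over 200, rise at least 70, stool test negative | Yes | Cross over | Cross over |
| CDAI 180, stool test negative | No (180 < 200, whatever the baseline) | Cross over | No route |
| CDAI over 200, rise at least 70, stool test positive | No (exception applies) | Cross over | No route |

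Row 1 is the gated case, and the sections agree. Row 2 arises under the ungated sentence. Row 3 is limited by 9.4.3, which defers an ileocolonoscopy not yet done until the infection has resolved. It therefore needs an endoscopy performed before the stool result was known. That can happen, because the Schedule of Activities places stool testing and ileocolonoscopy at the same flare visit.

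**Step 2: the route after Week 24.** Take an illustrative participant with baseline CDAI 60, Week 24 CDAI 110 with endoscopic recurrence and no crossover, and Week 32 CDAI 135.

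- Rise from baseline: 135 − 60 = 75, which meets 70.
- Rise from Week 24: 135 − 110 = 25, which does not.

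Eligibility turns on a reference value that the text does not give.

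**Step 3: consequences by endpoint.**

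- *Primary and first secondary.* Every disputed case has centrally read recurrence of i2a or worse. By Week 48 that is already a primary event and a first-secondary failure, with or without crossover.
- *Time to disease recurrence (third in the SAP hierarchy).* Crossover is not among the five intercurrent events in Protocol 9.4.3 or SAP Table 10. The censoring sentence in Protocol 9.4.3 and SAP 5.4.1.1 names endoscopic recurrence at Week 24 or Week 48 only. A flare-visit crossover without disease recurrence falls to the general rule, censoring at the last visit, so follow-up on open-label drug would count under the randomised arm. No ileocolonoscopy is scheduled between Week 48 and Week 152, and crossover stops after Week 128. In that stretch the flare visit is the main place where endoscopic recurrence without disease recurrence would be found. The plan expects a median follow-up of about 18 months. Week 48 is 48/52 × 12 ≈ 11 months, which leaves about 18 − 11 = 7 months of the median follow-up in that stretch.
- *Abdominal-pain-free status and steroid-free remission.* Crossover by Week 48 is a composite failure (SAP 5.4.1.2.3 and 5.4.1.2.5). The same participant kept on blinded drug could still succeed.
- *Time to recurrence of symptoms.* Follow-up is censored at crossover (SAP 5.4.1.1).

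**The case against.** The best defence is that the two operational sections, 6.5.1 and 8, agree with each other, that 8.1.3 refers back to 6.5.1, and that the shorter lists omit the flare route without forbidding it. With the CDAI gate, a positive flare endoscopy is normally disease recurrence anyway. This narrows the point but does not remove it. The ungated sentence in Section 8 and the pathogen exception still produce cases that cross over under one pair of sections and have no route under the others.

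Several stronger readings are tempting but not supported:

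- *Week 24 crossover is mandatory in one place and discretionary in another.* Every operative passage makes it discretionary. The risk table in 2.3.1 speaks of "endoscopic recurrence prior to or at Week 48, or, at the investigator's discretion, with endoscopic recurrence at Week 24". Its first phrase overlaps Week 24, but the same sentence makes Week 24 discretionary and cites 6.5.1. This is loose wording only. SAP 1.2.1 is also discretionary.
- *The post-Week 24 route contradicts 9.4.3.* It is a separate, permissive route for people whose Week 24 recurrence had already made them eligible. It need not match an endpoint definition.
- *Section 8.1.3 sets an absolute CDAI of 70.* The phrase is evidently a damaged form of the 6.5.1 sentence, possibly from text extraction, and not another rule.
- *Crossover is the only rescue in the trial.* Section 6.8.1 allows corticosteroids, AZA, 6-MP and MTX as rescue while study drug continues.
- *The share of participants affected can be estimated.* The documents give no CDAI distribution and no flare-endoscopy rate, so any percentage would rest on assumptions alone.

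One more concession: a participant with Week 24 recurrence who crosses over by Week 40 (24 + 16) can be read as covered by the censoring sentence, since the recurrence was found at Week 24. The gap is clear for flare-visit crossovers and only arguable for these.

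**Conclusion.** The crossover text is wrong as written on two points. The flare-visit route appears in two sections and is absent from five other lists. The optional route after Week 24 lacks a reference value for its CDAI rise and is garbled in 8.1.3.

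The divergence is confined to flare endoscopies done outside the CDAI gate or followed by a positive pathogen test. The primary and first secondary endpoints are largely protected through Week 48. What is exposed is time to disease recurrence, the three lower-ranked secondary endpoints that count or censor crossover, and the two crossover categories of major deviation, which cannot be judged consistently against differing criteria.

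The conclusion rests on the wording alone. SAP Section 1 reports that the study was discontinued with four participants enrolled and that the planned analyses no longer apply, so the present effect is small. The point would matter in full if the design or text were reused.

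**What to change.** 1. Reconcile Protocol 1.1, 4.1, 4.3, 6.5.1, 8, 8.1.3 and SAP 1.2.1 to one list of crossover routes in 6.5.1, cited everywhere else. For each route state the triggering assessment, whether crossover is mandatory or discretionary, and any CDAI condition with its reference value. Which clinical rule to keep is for the sponsor.
2. Correct the damaged sentence in 8.1.3, and tidy the overlap in 2.3.1 at the same time.
3. Record the crossover route on the eCRF, so that each crossover can be classified for the endpoints and for the deviation categories in SAP Appendix 4.
4. Extend the censoring rule for time to disease recurrence (Protocol 9.4.3, SAP 1.1 and 5.4.1.1) to every crossover without disease recurrence, not only those tied to Week 24 or Week 48.

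The cost is a protocol amendment, matching SAP edits and one eCRF field. A clarification communication would not be enough if the chosen rule changes conduct, because Protocol 10.3.1 limits those to text that leaves study conduct unchanged.
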